## 5 ETHICS

### 5.1 Institutional Review Boards/Independent Ethics Committees

The protocol, informed consent form (ICF), and appropriate related documents must be reviewed and approved by an Institutional Review Board (IRB) constituted and functioning in accordance with ICH E6 (Good Clinical Practice) and any local regulations. Any protocol amendment or revision to the ICF will be resubmitted to the IRB for review and approval, except for changes involving only logistical or administrative aspects of the study (eg, change in CRA[s], change of telephone number[s]). Documentation of IRB compliance with the ICH E6 and any local regulations regarding constitution and review conduct will be provided to the sponsor. A signed letter of study approval from the IRB chairman must be sent to the head of the medical institution) with a copy to the sponsor before study start and the release of any study drug to the site by the sponsor or its designee. If the IRB decides to suspend or terminate the study, the head of the medical institution will immediately send the notice of study suspension or termination by the IRB/IEC to the sponsor. Study progress is to be reported to IRBs annually (or as required) by the investigator or the head of the medical institution, depending on local regulatory obligations. The sponsor will submit, depending on local regulations, periodic reports and inform the IRB, the investigator and the relevant IRB via the head of the medical institution) of any reportable adverse events (AEs) per GCP guidelines and local IRB standards of practice. Upon completion of the study, the investigator will provide the IRB with a brief report of the outcome of the study, if required.

### 5.2 Ethical Conduct of the Study

This study will be conducted in accordance with standard operating procedures of the sponsor (or designee), which are designed to ensure adherence to GCP guidelines as required by the following:

- Principles of the World Medical Association Declaration of Helsinki
- GCP
- Article 14, Paragraph 3, and Article 80-2 of the Pharmaceuticals, Medical devices and Other Therapeutic Products Act (Law No. 145, 1960) for studies conducted in Japan, in addition to Japan's GCP

### 5.3 Subject Information and Informed Consent

As part of administering the informed consent document, the investigator must explain to each subject (or guardian/legally authorized representative) the nature of the study, its purpose, the procedures involved, the expected duration, the potential risks and benefits involved, any potential discomfort, potential alternative procedure(s) or course(s) of treatment available to the subject, and the extent of maintaining confidentiality of the subject's records. Each subject must be informed that participation in the study is voluntary,

that he/she may withdraw from the study at any time, and that withdrawal of consent will not affect his/her subsequent medical treatment or relationship with the treating physician.

This informed consent should be given by means of a standard written statement, written in nontechnical language. The subject or the subject's legally acceptable representative should understand the statement before signing and dating it and will be given a copy of the signed document. If a subject is unable to read or if a legally acceptable representative is unable to read, an impartial witness should be present during the entire informed consent discussion. After the ICF and any other written information to be provided to subjects is read and explained to the subject or the subject's legally acceptable representative, and after the subject or the subject's legally acceptable representative has orally consented to the subject's participation in the study and, if capable of doing so, has signed and personally dated the ICF, the witness should sign and personally date the consent form. The subject will be asked to sign an ICF before any study-specific procedures are performed. No subject can enter the study before his/her informed consent has been obtained. An unsigned copy of an IRB-approved ICF must be prepared in accordance with GCP, and all applicable local regulations. Each subject must sign an approved ICF before study participation. The form must be signed and dated by the appropriate parties. The original, signed ICF for each subject will be verified by the sponsor and kept on file according to local procedures at the site. The subject should be informed in a timely manner if new information becomes available that may be relevant to the subject's willingness to continue participation in the study. The communication of this information should be documented.

## **6 INVESTIGATORS AND STUDY PERSONNEL**

This study will be conducted by qualified investigators under the sponsorship of Eisai (the sponsor) at three to five investigational sites in Japan. The name and telephone and fax numbers of the sponsor are listed in the Appendix 3.

## 7 INTRODUCTION

### 7.1 Indication

Renal Cell Carcinoma (RCC) is a rare tumor type representing 3% of all cancers in adults, accounting for 90% of the total renal cancers (National Comprehensive Cancer Network, 2015). In 2012, estimate of the worldwide incidence of renal cancers (renal pelvis and ureters included) was 330,000 of which 210,000 were men and 120,000 were women. The total of 140,000 deaths was estimated to have occurred, of which 90,000 were men and 50,000 were women (Ferlay J, et al., 2015). In Japan, annual incidence of renal cancers (renal pelvis, ureters, and other unknown site in the urinary system are included) is approximately 18,000 and the number of death (renal pelvis, ureters, and other unknown site in the urinary system are excluded) is approximately 4,500 (Foundation for Promotion of Cancer Research, 2013). There are three main histologic types of renal cell carcinoma; clear cell-type tumors account for approximately 80% of RCC, followed by papillary type (10 to 15%), and chromophobe cell type (3 to 5%) (National Comprehensive Cancer Network, 2015., Rini BI, et al., 2009). The risk factors for RCC include obesity, smoking, hypertension, dialysis treatment, and von Hippel-Lindau disease. When a patient is initially diagnosed with RCC, localized tumor is present in 45% of cases, followed by 30% of metastasis, and 25% of locally-advanced tumor. The prognosis is poor at stage IV with locally-advanced or distant metastasis, with only 10% of 5-year survival (Molina AM and Motzer RJ, 2008, Motzer RJ, et al., 1996, National Cancer Center, Department of Internal Medicine, 2013). The treatment options for RCC are surgery and/or anti-cancer medication, depending on the disease stage. Anti-cancer medication commonly used to treat unresectable or metastatic RCC include: agents targeting vascular endothelial growth factor (VEGF) and VEGF receptor (VEGFR) such as bevacizumab, sunitinib, sorafenib, pazopanib, axitinib, and agents targeting mammalian target of rapamycin (mTOR) such as tamsinrolimus and everolimus (National Comprehensive Cancer Network, 2015., Escudier B, et al., 2014). Cytokine (eg, interferon) has been widely used in the treatment of RCC but tyrosine kinase inhibitors (TKI) that block VEGFR, such as sunitinib and pazopanib, are administered as the first-line treatment in recent years. Type of second-line and subsequent treatments vary depending on the drug administered in the previous treatment. Among these available agents, everolimus was confirmed to be efficacious with 1.8% ORR, median PFS of 4.9 months, and overall OS of 14.8 months when administered to metastatic RCC patients with disease progression following sunitinib or sorafenib treatment (Motzer RJ, et al., 2008). In a phase 3 study comparing the efficacy of axitinib and sorafenib as second-line treatment in RCC subjects who previously received cytokine or sunitinib treatment, axitinib demonstrated higher efficacy with the ORR 23.0% (12.0% for sorafenib), median PFS 6.7 months (4.7 months for sorafenib), and median OS 20.1 months (19.2 months for sorafenib) (Rini BI, et al., 2011).

Based on above findings, axitinib or everolimus would likely be the second-line treatment option for RCC patients who were previously treated with TKI. Although many treatment options are available for patients with incurable, unresectable or advanced RCC, the

prognosis remains poor and development of new agents and treatment to improve clinical outcome of the second or third line treatments are anticipated.

## 7.2 Lenvatinib Mesylate (Lenvatinib)

VEGFR is expressed in vascular endothelial cells, playing a vital role for physiological and pathological angiogenesis and lymphogenesis or in the malignant cells led by VEGF ligand stimulation (Ellis LM and Hicklin DJ, 2008, Ferrara N, et al., 2003, Hattori K, et al., 2002, Laakkonen P, et al., 2007, Tammela T and Alitalo K, 2010). Fibroblast growth factors receptor (FGFR), platelet-derived Growth Factor receptor- $\alpha$  (PDGFR $\alpha$ ), RET, and KIT are also known to be associated with angiogenesis, proliferation, or both (St Bernard, et al., 2005, Turner and Grose, 2012, Matsui, et al., 2004, Hirota, et al., 1998, Williams, 2002, Kondo, et al., 2006, Phay and Shah, 2010, Gild, et al., 2011, Hirota, et al., 2003, Oseini and Roberts, 2009) and an effective anticancer treatment may be established if their receptors, tyrosine kinases (RTKs) are inhibited simultaneously. Lenvatinib Mesylate (E7080) was developed at Eisai Tsukuba Research Laboratories to explore agents that inhibit RTKs activities associated with tumor angiogenesis. It is a multikinase inhibitor that exhibits potent inhibitory effects not only on VEGFR1 to VEGFR 3 at the level of inhibition constant  $K_i$  1 nmol/L, but also on FGFR 1 to FGFR4 and KITs. In nonclinical studies, lenvatinib showed inhibitory activities dose-dependently in VEGFR2-driven phosphorylation, tube formation and proliferation in human vascular endothelial cells (human umbilical vein endothelial cell – HUVEC) induced by VEGF. In vivo study where human cancer cells are transplanted in immune deficient mouse models, lenvatinib also demonstrated high anticancer effect in a wide variety of cancers including RCC. In addition, safety results in non-clinical studies showed lenvatinib was well tolerated within the therapeutic range. Three phase 1 studies were conducted in Japan, US, and Europe with different regimen to determine the safety, tolerability and pharmacokinetics of lenvatinib. Treatment regimen for each study was: continuous once daily for E7080-E044-101 (Europe), continuous twice daily for E7080-A001-102 (US), and twice daily for 2 weeks with dosing intervals of one week for E7080-J081-103 (Japan). Based on the results from these studies, a continuous dose of 24 mg once daily has been selected to treat solid tumors for ongoing lenvatinib development. The tolerability in 24 mg once daily continuous dose in Japanese subjects was confirmed in another study conducted in Japan (E7080-J081-105). There was no significant difference in tolerability and pharmacokinetics among subjects in Japan, Europe, and US. lenvatinib is expected to be efficacious regardless of cancer type; clinical studies are being conducted for various solid malignancies including thyroid carcinoma, hepatocellular carcinoma, RCC, non-small-cell lung cancer, endometrial cancer, glioma, malignant melanoma, and ovarian cancer. Based on the results from Phase 2 studies conducted in Japan and overseas, and multi-center global Phase 3 studies, lenvatinib was approved in February 2015 for the treatment of patients with locally recurrent or metastatic, progressive radioiodine refractory differentiated thyroid cancer. Approvals in Europe and Japan are also underway in 2015.

### 7.3 Concomitant use of Lenvatinib and Everolimus for RCC patients

Common treatment options for RCC patients include VEGF, VEGFR, or mTOR target agents as first or second-line treatment. However, most patients do not respond well and become resistant to the currently available drugs, resulting in disease progression. Therefore, combination of lenvatinib and everolimus to simultaneously inhibit VEGF and mTOR signaling pathways seem logical as they both play a key role in exacerbation and development of resistance. The treatment is expected to enhance effectiveness of each agent and overcome treatment-resistance.

As of today, combination therapy of existing TKI agent and mTOR inhibitor is yet to be approved.

#### 7.3.1 Everolimus

Everolimus inhibits mTOR, a type of serine/threonine protein kinase. It is known that mTOR is a downstream factor of PI3K/Akt, comprising PI3K/Akt/mTOR signaling pathway. Functional abnormalities of molecules comprising this pathway are associated with various human cancer pathophysiology and have been confirmed for its significance in tumor genesis (Seeliger H, et al., 2007). Everolimus blocks intercellular signaling by inhibiting mTOR. This is believed to suppress proliferation, VEGF production by tumor cell, and proliferation of vascular endothelial cells, thereby controlling neoangiogenesis and exert anticancer effect. In Japan, everolimus has been approved for following conditions: unresectable, non-curable or metastatic RCC, pancreatic neuroendocrine tumors, unresectable or recurrent breast cancer, renal angiomyolipoma associated with nodular sclerosis, subependymal giant cell astrocytoma associated with nodular sclerosis.

#### 7.3.2 Overseas Phase 1/2 study

Phase 1 and 2 studies (Study 205) were conducted to compare efficacy and safety of lenvatinib alone, everolimus alone, or combination of the two when administered to advanced or metastatic RCC patients following prior VEGF-targeted treatment.

##### 7.3.2.1 Phase 1 part

In Phase 1 part, the dose limiting toxicity (DLT) and maximum tolerated dose (MTD) of lenvatinib was determined when administered in combination with everolimus in subjects with unresectable advanced or metastatic RCC following prior VEGF-targeted treatment. Recommended dose of lenvatinib in combination with everolimus for Phase 2 was also determined (Molina AM, et al., 2014).

One treatment cycle was defined as 28 days. Lenvatinib was administered at starting dose of 12 mg/day in combination with everolimus at starting dose of 5 mg/day (Cohort 1). Lenvatinib was subsequently titrated to 18 mg/day (Cohort 2) and 24 mg/day (Cohort 3) while starting dose of everolimus (5mg/day) was maintained. In Cohort 4, everolimus was

titrated to 10 mg/day. Subjects were enrolled in the treatment group at which MTD was determined, up to the minimum of 10 subjects.

Number of subjects enrolled in Cohorts 1, 2, and 3 were 7, 11, and 2, respectively.

DLTs seen in each cohort were: one subject in Cohort 1 (Grade 3 abdominal pain), one subject in Cohort 2 (Failure to administer  $\geq 75\%$  of planned dose due to Grade 3 increased creatine phosphokinase, Grade 2 fatigue, Grade 1 gastroesophageal reflux disease), two subjects in Cohort 3 (Grade 3 nausea and vomiting [1 subject], (Failure to administer  $\geq 75\%$  of planned dose due to Grade 2 stomatitis [1 subject])). Cohort 4 was not treated. Based on these findings, recommended doses for combination therapy in Phase 2 were determined to be lenvatinib 18 mg/day and everolimus 5 mg/day.

#### 7.3.2.2 Phase 2 part

In Phase 2 part, subjects with unresectable advanced or metastatic RCC with disease progression following one prior VEGF-targeted treatment were randomized to one of the following treatment groups to compare the safety and efficacy. Primary endpoint was PFS.

- Arm A : envatinib 18 mg + everolimus 5 mg
- Arm B : lenvatinib 24 mg
- Arm C : everolimus 10 mg

#### **Efficacy**

Number of subjects assigned to each treatment groups were: 51 subjects for Arm A, 52 subjects for Arm B, and 50 subjects for Arm C. PFS in Arms A and B were prolonged as compared with Arm C. Median PFS of Arms A, B, and C were 14.6 months, 7.4 months, and 5.5 months, respectively. Hazard ratio (HR) of Arm A to Arm C was 0.40,  $P < 0.001$ , and that of Arm B to Arm C was 0.61,  $P = 0.048$ . ORR of each treatment group was 43.1% (Arm A), 26.9% (Arm B), and 6.0% (Arm C). Median overall survival (OS) of Arm A, Arm B and Arm C was 25.5 months, 18.4 months, and 17.5 months, respectively. Hazard ratio (HR) of Arm A to Arm C was 0.55,  $P = 0.062$ , and that of Arm B to Group C was 0.74,  $P = 0.290$ .

#### **Safety**

Treatment-emergent adverse events (TEAE) experienced by  $\geq 20\%$  of subjects in Arm A were: diarrhea, decreased appetite, fatigue, vomiting, hypertension, nausea, cough, hypertriglyceridaemia, hypercholesterolaemia, weight decreased, stomatitis, oedema peripheral, arthralgia, asthenia, dyspnea, hypothyroidism, proteinuria, and pyrexia. Grade 3 or higher TEAEs experienced by  $\geq 5\%$  of subjects in Arm A were: diarrhea, hypertension, fatigue, anaemia, hypertriglyceridaemia, vomiting, decreased appetite, dehydration, nausea, and thrombocytopenia. Grade 3 or higher TEAEs that were seen more often in Arm A than in Arms B or C by  $\geq 2$  subjects were: diarrhea, fatigue, vomiting, dehydration,

thrombocytopenia, back pain, and general physical health deterioration. Serious TEAEs (SAE) experienced by  $\geq 5\%$  of subjects in Arm A were: anaemia, thrombocytopenia, diarrhea, and dehydration. SAEs that were seen more often in Arm A than in Arms B or C by  $\geq 2$  subjects were: thrombocytopenia, diarrhea, dehydration, vomiting, hyperkalaemia, general physical health deterioration, and renal impairment. An AE that resulted in subject death was cerebral haemorrhage. Following events were more frequently observed in Arm A than in Arms B or C: diarrhea, fatigue, vomiting, dehydration, thrombocytopenia, back pain, general physical health deterioration, hyperkalaemia, and renal impairment. In general, they were all manageable by administering symptomatic treatment, dose interruption, or dose reduction of study drugs. The safety profile of combination treatment group (Arm A) was generally similar to those of single-agent treatment Arms (B and C), and no newly discovered safety concerns were reported. Above results demonstrated that improved prolongation of PFS and OS can be expected in combination treatment of lenvatinib 18 mg/day and everolimus 5mg/day, compared with everolimus single-agent treatment. Although adverse drug reactions were observed in some patients they were manageable, therefore this combination therapy seemed promising for unresectable advanced or metastatic RCC with disease progression following prior one VEGF-target treatment.

#### 7.4 Expected Adverse Events

For lenvatinib, important identified risk include: hypertension, hemorrhage, arterial thromboembolism, venous thromboembolism, liver disorder, renal disorder, gastrointestinal perforation/fistula, posterior reversible encephalopathy syndrome, cardiac disorder, hand and foot syndrome, infections, bone-marrow suppression, hypocalcaemia, delayed wound healing. Lenvatinib should be administered with caution to the patients with hypertension, severe liver disorder, cerebral metastasis, thromboembolism or history of thromboembolism, and incomplete wound healing following surgical procedure. Close monitoring are required after lenvatinib administration for: hypertension, uric protein, bone-marrow suppression, liver disorder associated with increased AST or ALT, cardiac dysfunction, delayed wound healing, fatigue and apathy, dizziness, muscle spasms, serum calcium concentration, and level of thyroid-stimulating hormone. For everolimus, important identified risk include: interstitial lung disease, infections, renal failure, hyperglycemia, development or exacerbation of diabetes, anemia, decreased hemoglobin, decreased leukopenia, decreased lymphopenia, decreased neutropenia, and thrombocytopenia, stomatitis, anaphylaxis, acute respiratory distress syndrome, malignancy (secondary), progressive multifocal leukoencephalopathy, BK virus nephropathy, thrombotic microangiopathy, pulmonary alveolar proteinosis, and pericardial effusion.

Everolimus should be administered with caution to patients with current conditions or history of interstitial pulmonary shadow, comorbid infections, liver dysfunction or hepatitis virus, tuberculosis, and elderly patients. Close monitoring will be required following administration of everolimus for: interstitial pulmonary disease, infection or opportunistic infection from bacteria, fungi, viruses, protozoa, severe renal disorder, hyperglycemia, decreased hemoglobin, decreased lymphopenia, decreased neutropenia, decreased platelet. In overseas study (Study 205), Grade 3 or higher cases of diarrhea, fatigue, vomiting, dehydration, thrombocytopenia, back pain, general physical health deterioration, hyperkalaemia, and renal impairment are more frequently seen in lenvatinib-everolimus combination therapy compared to

single-agent therapy each. Cautions should be exercised as effects on adverse events can be potentiated by co-administering the two agents.

## 7.5 Study Rationale

This is a Phase 1 study of lenvatinib in combination with everolimus in Japanese subjects with unresectable advanced or metastatic RCC. Lenvatinib will be administered at starting dose of 18 mg in combination with everolimus at starting dose of 5 mg both orally once daily continuously. DLT will be observed during Cycle 1 (28 days following the initial dosing) to determine the tolerability and safety. Treatment will continue until disease progression, development of intolerable toxicity, subject requests to discontinue, withdrawal of consent, or study termination by sponsor. The same regimen, lenvatinib 18 mg/day and everolimus 5 mg/day, will be employed based on the results obtained in the overseas study (Study 205) and is also considered for future global studies including Japan. Single-agent treatment of lenvatinib was tolerated up to the dose of 24 mg/day continuous administration in Japanese patients with solid tumor and similar results were observed in Europe and US. Everolimus has been approved in Japan, US, and Europe, for treatment of RCC patients at dose of 10 mg/day once daily continuous administration. No significant difference in tolerability has been noted between Japanese and non-Japanese patients. However, this combination regimen has never been studied in Japan; the tolerability and pharmacokinetics in Japanese patients are unknown.

For this reason, this study was considered scientifically rational and designed based on the previous findings to evaluate the tolerability, safety, and pharmacokinetics of lenvatinib- everolimus combination therapy.

## **8 STUDY OBJECTIVES**

### **8.1 Primary Objective**

- To investigate tolerability and safety of lenvatinib in combination with everolimus in subjects with unresectable advanced or metastatic renal cell carcinoma (RCC)

### **8.2 Secondary Objectives**

- To assess the pharmacokinetic (PK) of lenvatinib and everolimus
- To assess the preliminary anticancer effects of lenvatinib in combination with everolimus

## **9 INVESTIGATIONAL PLAN**

### **9.1 Overall Study Design and Plan**

This is a non-randomized, open-label, multi-center Phase 1 study (E7080-J081-112) of lenvatinib in combination with everolimus in subjects with unresectable advanced or metastatic RCC. Subjects will be enrolled in this study after informed consent is obtained and eligibility is confirmed.

One treatment cycle is defined as 28 days. Lenvatinib will be administered at starting dose of 18 mg in combination with everolimus at starting dose of 5 mg both orally once daily continuously. DLT will be observed during Cycle 1 (28 days following the initial dosing) to investigate tolerability and safety. Treatment will continue until disease progression, development of unacceptable toxicity, subject requests to discontinue, withdrawal of consent, or study termination by sponsor.

A total of six subjects will be initially enrolled. Enrollment will be interrupted when DLT is observed in two or more subjects. Investigators and sponsor will review the nature and severity of all the DLTs and make a decision if enrollment of up to six subjects and further additions of three to six subjects are feasible and necessary. Suggestions by the independent medical advisor will be collected, if necessary.

The study sponsor and investigators will consider the nature and severity of DLT during Cycle 1 as well as unacceptable toxicities that cannot be managed with dose interruption and/or reduction and overall toxicities up to Cycle 2 on the evaluation of tolerability in combination therapy. The suggestions by the independent medical advisor can be collected, if necessary.

Additional subjects may be enrolled to the lower cohort (lenvatinib 14 mg and everolimus 5 mg once daily administration) in the following cases: over one-third of subjects experiences DLTs during Cycle 1, development of unacceptable, development of unmanageable toxicity with dose interruption and/or reduction up to Cycle 2, tolerability cannot be confirmed with dose level of lenvatinib 18 mg/everolimus 5 mg QD.

If a subject has no DLT but fails to receive  $\geq 75\%$  of the planned dosage of lenvatinib and/or everolimus up to Cycle 1 Day 21, due to a reason other than treatment related toxicity, this subject will not be included in the DLT assessment population and a new subject will be added for replacement.

[figure not shown]
Subjects will discontinue study treatment at the time of disease progression, development of unacceptable toxicity, withdrawal of consent, or qualifies any of the criteria described in '9.3.3.1 Discontinuation for Individual Subjects'. The discontinuation assessments will occur within 7 days and off-treatment visit on 30th day after the final dose of study treatment.

DLT is defined as toxicity related to this combination therapy as indicated below.

Table 1. Dose Limiting Toxicities (DLT)

Toxicity Category	Toxicity/CTCAE Grade
Hematologic	
 
• Grade 4 neutropenia lasting >7 days
 
• Grade 3 febrile neutropenia (axillary temperature <math>\geq 38.5^{\circ}\text{C}</math> and neutrophils <math>< 1 \times 10^3/\mu\text{L}</math> (<math>< 1000/\text{mm}^3</math>))
 
• Grade <math>\geq 3</math> thrombocytopenia lasting >7 days or requiring blood transfusion
 

Non-hematologic toxicity	
 
• Grade 3 non-hematologic toxicities lasting >7 days except for the following: 
 
➢ Clinically insignificant or transient abnormal laboratory findings
 
➢ Able to be controlled by maximal supportive therapy
 
 Grade <math>\geq 3</math> hyperamylasemia or hyperlipasemia without clinical or other evidence of pancreatitis are not regarded as a DLT. 
 
• Grade <math>\geq 3</math> Nausea, vomiting or diarrhea lasting >7 days despite maximal medical therapy
 
• Hypertension uncontrolled by medication
 
• Any thromboembolic event including cerebrovascular hemorrhage/events
 

Medication compliance	
 
• Failure to administer <math>\geq 75\%</math> of the planned dosage of lenvatinib or everolimus as a result of treatment related toxicity
 

Overall study design is presented below.

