If a subject has no DLT and fails to administer  $\geq 75\%$  of the planned dosage of lenvatinib and/or everolimus as a result of a reason other than treatment related toxicity up to Cycle 1 Day 28, this subject will not be included in the DLT assessment population and another subject will be added for replacement. Investigator and sponsor will make a decision for selection of subject to be included in DLT assessment population and additional subject will be considered as needed. DLT is defined as toxicity related to this combination therapy of the following indicated in below Table. **Table : Dose Limiting Toxicities (DLT)**

Toxicity Category	Toxicity/CTCAE Grade
Hematologic	
 
• Grade 4 neutropenia lasting >7 days
 
• Grade 3 febrile neutropenia (axillary temperature <math>\geq 38.5^\circ\text{C}</math> and neutrophils <math>< 1 \times 10^3/\mu\text{L}</math> (<math>< 1000/\text{mm}^3</math>))
 
• Grade <math>\geq 3</math> thrombocytopenia lasting >7 days or requiring blood transfusion
 

Non-hematologic toxicity	
 
• Grade 3 non-hematologic toxicities lasting >7 days except for the following: 
 
➤ Clinically insignificant or transient abnormal laboratory findings
 
➤ Able to be controlled by maximal supportive therapy
 
 
 
• Grade <math>\geq 3</math> hyperamylasemia or hyperlipasemia without clinical or other evidence of pancreatitis are not regarded as a DLT.
 
• Grade <math>\geq 3</math> Nausea, vomiting or diarrhea lasting >7 days despite maximal medical therapy
 
• Hypertension uncontrolled by medication
 
• Any thromboembolic event including cerebrovascular hemorrhage/events
 

Medication compliance	
 
• Failure to administer <math>\geq 75\%</math> of the planned dosage of lenvatinib or everolimus as a result of treatment related toxicity
 

Number of Subjects

6 to 12 (planned)

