**Statistical Methods****Analysis Sets**

DLT Analysis Set is the group of subjects who have completed treatment Cycle 1 without major protocol deviation with at least 75% of treatment compliance and were assessed for DLT, and subjects who have experienced DLT during Cycle 1. Subjects with less than 75% treatment compliance to lenvatinib or everolimus due to a reason other than toxicity up to Cycle 1 Day 28 will not be included in this analysis set. Safety Analysis Set/Efficacy Analysis Set is the group of subjects who received at least 1 dose of lenvatinib. Pharmacokinetic (PK) Analysis Set is the group of subjects who received at least 1 dose of lenvatinib and had sufficient PK data to derive at least one PK parameter.

Following analysis will be performed for total subjects or by initial dose group (if applicable).

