5.2 Study Subjects

5.2.1 Definitions of Analysis Sets

DLT Analysis Set is the group of subjects who have completed treatment Cycle 1 without major protocol deviation with at least 75% of treatment compliance and were assessed for DLT, and subjects who have experienced DLT during Cycle 1. Subjects with less than 75% treatment compliance to lenvatinib or everolimus due to a reason other than toxicity up to Cycle 1 Day 28 will not be included in this analysis set.

Safety Analysis Set/Efficacy Analysis Set is the group of subjects who received at least 1 dose of lenvatinib

Pharmacokinetic Analysis Set is the group of subjects who received at least 1 dose of lenvatinib and had sufficient PK data to derive at least 1 PK parameter.

The number of subjects enrolled, the number and the percentage of subjects included in each analysis set will be presented. Subject data listings will be provided.

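### The rule for replacing under-dosed subjects uses Cycle 1 Day 21 in Protocol 9.1 and SAP 3.2.1, but the synopsis and every DLT Analysis Set definition use Day 28

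*Protocol*

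**What the plan says.** The compliance rule for DLT evaluability is stated six times, with two different days.

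- **Day 21.** Protocol 9.1 says of a subject without DLT who falls short of 75% of planned dosage: "up to Cycle 1 Day 21, due to a reason other than treatment related toxicity, this subject will not be included". SAP 3.2.1 repeats this. Both then require a replacement, without qualification.
- **Day 28, replacement rule.** The synopsis (Study Design) applies the rule to "a reason other than treatment related toxicity up to Cycle 1 Day 28, this subject will not be included in the DLT assessment population". It alone adds that the investigator and sponsor decide on "selection of subject to be included in DLT assessment population and additional subject will be considered as needed".
- **Day 28, analysis set.** The synopsis (Analysis Sets), Protocol 9.7.1.2 and SAP 5.2.1 all leave out of the DLT Analysis Set "Subjects with less than 75% treatment compliance to lenvatinib or everolimus due to a reason other than toxicity up to Cycle 1 Day 28". Apart from those who had a DLT, members must have "completed treatment Cycle 1 without major protocol deviation with at least 75% of treatment compliance and were assessed for DLT".

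The DLT window is the full cycle: "DLT will be observed during Cycle 1 (28 days following the initial dosing) to investigate tolerability and safety". DLT is a primary endpoint (Protocol 9.7.1.1, SAP 5.1.1), and tolerability is analysed on the DLT Analysis Set (Protocol 9.7.1.9, SAP 5.6). SAP Section 7, which lists changes from the protocol, does not mention the day.

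**The concern.** A replacement rule in a six-subject cohort exists to keep the analysed set at its intended size. That works only if replacement and membership of the set use the same test. Here the set has one consistent definition, but the rule meant to refill it is written with an earlier cut-off in the body of the protocol and in the SAP. A subject can then be lost from the analysis without being replaced, or be replaced while still meeting the set's compliance criterion.

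What is at stake is the denominator of the primary DLT rate. It matters most beside the guide for opening the lower cohort, "over one-third of subjects experiences DLTs during Cycle 1", because two DLTs in six subjects sit exactly at one-third.

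**Working it through.** There is no power or sample-size figure to reproduce: Protocol 9.7.2 and SAP Section 4 say that the size has no statistical basis. The check is a count of dosing patterns.

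**Inputs.** One planned dose per day for 28 days. Let *d* be the doses taken in Days 1–21 (0 to 21) and *e* the doses taken in Days 22–28 (0 to 7), which gives 22 × 8 = 176 combinations. The count is for one drug, missed doses are for reasons other than toxicity, and the subject has no DLT. Protocol 9.4.1 bars dose reduction in Cycle 1 without a DLT, so the share of doses equals the share of planned dosage. The same section allows interruption and resumption in Cycle 1.

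**Set's compliance test (Day 28).** Fails if (*d* + *e*)/28 < 0.75, that is, fewer than 21 doses.

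**Replacement test (Day 21).** The text does not say what the 75% is taken of, so there are two readings:

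- Reading (a), 75% of the 21 doses due by Day 21: 0.75 × 21 = 15.75, so a subject with fewer than 16 doses is replaced.
- Reading (b), 75% of all 28 doses: 0.75 × 28 = 21, so a subject with fewer than 21 doses by Day 21 is replaced. A single missed dose is enough.

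**Not replaced, yet outside the Set**

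- Reading (a): *d* = 16 with *e* = 0–4; 17 with 0–3; 18 with 0–2; 19 with 0–1; 20 with 0. That is 5 + 4 + 3 + 2 + 1 = 15 patterns.
- Five of these have *e* = 0 (stopping after 16–20 doses) and also fail the requirement to complete Cycle 1. The other 10 include dosing in Days 22–28. Example: 18/21 = 85.7%, then 2 of 7, total 20/28 = 71.4%.
- Reading (b): none, because *d* must be 21 and the Day 28 test is then already met.

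**Replaced, yet meeting the Set's 75% test**

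- Reading (a): (14, 7), (15, 6) and (15, 7), so 3 patterns. Example: 15/21 = 71.4%, then 7 of 7, total 22/28 = 78.6%.
- Reading (b): *d* = 14 to 20 with *e* at least 21 − *d*, so 1 + 2 + … + 7 = 28 patterns. With every later dose taken, this means 1 to 7 missed doses.

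| Replacement rule | Not replaced, outside Set | Replaced, meets Set's 75% test |
|---|---|---|
| Day 21, reading (a) | 15 | 3 |
| Day 21, reading (b) | 0 | 28 |
| Day 28, 75% of 28 doses | 0 | 0 |

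**Effect on the DLT rate**, taking the Set as denominator. The fewest DLTs that exceed one-third of *n* is floor(*n*/3) + 1.

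| *n* | 5 | 6 | 7 | 9 | 10 | 12 | 13 |
|---|---|---|---|---|---|---|---|
| Fewest DLTs over one-third | 2 | 3 | 3 | 4 | 4 | 5 | 5 |

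- One unreplaced loss from six, reading (a) only: 2/6 = 33.3% becomes 2/5 = 40.0%, which is over one-third.
- One extra subject kept, either reading: 2/6 becomes 2/7 = 28.6%. The percentage changes, but the count needed to exceed one-third stays at 3. The same holds for 9 against 10 and for 12 against 13.

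**The case against.** The strongest reply is that the analysis itself is not in doubt. All three definitions of the DLT Analysis Set agree on Day 28, so nobody needs Day 21 to compute the DLT rate. That is correct: the fault lies in the replacement rule, not in the Set.

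Second, the consequences are soft. The one-third text does not name its denominator, so setting 2/5 against it assumes the Set is meant. The lower cohort is only an option, no judgment criteria are set, and "Enrollment will be interrupted when DLT is observed in two or more subjects" brings a review whatever the denominator. All of this stands, and it limits the point to a correction of wording with a small practical effect.

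Third, the synopsis lets the investigator and sponsor add a subject as they see fit, which could cover an unreplaced loss. That helps only in part. The provision is absent from Protocol 9.1 and SAP 3.2.1, where replacement is unconditional. In an open-label trial, discretion over a primary-endpoint denominator is also a reason to have one clear rule.

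Fourth, a subject removed under the Day 21 sentence might be treated as not assessed for DLT and so as outside the Set, which would remove the 2/7 case. The Set's own wording does not say this. A subject who completes Cycle 1 without major deviation, reaches 75% by Day 28 and is assessed belongs to it. The two sections then give opposite answers for the same person.

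Fifth, reading (b) is strained, and the pattern counts are not probabilities. Both points are fair. The counts show that the mismatch exists on either reading, not how often it would occur.

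**Conclusion.** The concern holds. Both days stand in the current protocol and in the current SAP, and on either reading of the 75% the Day 21 replacement rule classifies some subjects differently from the Set on which the primary DLT rate is reported.

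The practical effect is small. Only an unreplaced loss, possible under reading (a) alone, can move a result across one-third (2/6 to 2/5), and only if the Set is the intended denominator. The opposite mismatch changes the reported percentage but not whether one-third is exceeded. No DLT rate or loss rate was assumed. The contradiction itself is certain from the text and should be corrected before DLT outcomes are known.

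**What to change.** In Protocol 9.1 and SAP 3.2.1, change the cut-off to Cycle 1 Day 28. State there that the 75% is of the dosage planned for the 28-day cycle. This matches the 28-day DLT window and the other four statements of the rule, and it removes every mismatch on the compliance criterion.

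It does not cover every DLT-free subject outside the Set. One who stops after 21–27 doses meets 75% but has not completed Cycle 1, and one with a major deviation is also excluded. These cases stay under the synopsis provision for adding a subject as needed; extending automatic replacement to them is optional.

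The cost is a one-line correction in each document and, at most, an occasional extra replacement subject, which the synopsis already foresees.
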